## Document History

Document	Version Date	Summary of Changes and Rationale
Original protocol	06 September 2023	N/A
Amendment 1	20 March 2024	
Global Amendment: The rationale for the amendment is related to the PART 1 questions received from the EU CTA, submitted 27 Nov 2023.
 
Cover Page of the protocol and synopsis: added the NCT number. Justification: removed TBD.
 
Section 1.0, Schedule of assessments, added abbreviations under the SOA, and Tables 1, 2,3, and 4 Justification: To provide protocol clarity based on the responses to the questions received from EU CTA review.
 
Section 4.3, Justification for dose; updated with information to support dose frequency. Justification: To provide protocol clarity based on the responses to the questions received from EU CTA review.
 
Section 8.2.4.1, Histology assessments; updated section to provide approximate rate of screen failures related to histology requirements. Justification: To provide protocol clarity based on the responses to the questions received from EU CTA review.
 
Section 8.4.4, Regulatory reporting requirements for serious adverse events, SAEs; Updated section with regulatory authorities US FDA, and EU Eudra Vigilance.

Document	Version Date	Summary of Changes and Rationale
		
Justification: To provide protocol clarity based on the responses to the questions received from EU CTA review.
 
Section 9.5, Interim Analyses, (IA) and synopsis updated to provide rationale for having the IA.
 
Justification: To provide protocol clarity based on the responses to the questions received from EU CTA review.

		
Section 9.6 and synopsis Sample size determination; corrected a typo from 99% to 94% approximate power, and 0.4 to 0.5 for standard deviation.
 
Added dropout rate of 30% to determine a difference of 0.5 evaluable subjects, in the full analysis set.
 
Justification: To provide protocol clarity based on the responses to the questions received from EU CTA review.

		
Section 10.0, Appendix 1, Supporting documentation and operational considerations; Updated section with, “In addition to the safety reporting responsibilities to the Sponsor in Section 10.3.4, and in accordance with local regulations.”
 
Justification: To provide protocol clarity based on the responses to the questions received from EU CTA review.

		
Appendix 9.0, Infusion- related reactions; updated, If the reaction has not resolved within “6 hours of study drug preparation”, also added In

Document	Version Date	Summary of Changes and Rationale
		
cases where infusion has started but cannot be completed with 6 hours of study drug preparation, the remainder of the infusion will not be administered and study intervention will be permanently discontinued.
 
Justification: To provide protocol clarity based on the responses to the questions received from EU CTA review.

		
Section 10.1.11, Publication policy, updated to see section 10.1.6
 
Justification: To provide protocol clarity based on the responses to the questions received from EU CTA review.

		
References, Section 11.0, added reference Adelman DC, Murray J, Wu TT, et al. Measuring change in small intestinal histology in patients with celiac disease. The American Journal of Gastroenterology. 2018. 113:339-47.

		
Justification: To provide protocol clarity based on the responses to the questions received from EU CTA review.

		
Section 10.1.12 Sponsor's Medically Qualified Individual; updated to replace emergency contact cards with a study information card.

		
Justification: The process for contacting a medically qualified individual has changed from a medical escalation process via a Pfizer Call Center to direct clinical

Document	Version Date	Summary of Changes and Rationale
		
team contact using a Study Team Contact List
 
Inclusion of PACL 1; Dated 05 January 2024; Section 5.0, Inclusion criteria #4 updated to match the synopsis. Removed details about laboratory ranges as not needed, also updated Appendix 2, Table 3; protocol required lab assessments
 
Justification: Due to differences in lab ranges, it was decided to go with the lab labels, of negative and weak positive.
 
Typos corrected.

		
Section 5.2 Clarified Exclusion Criteria 12
 
Justification: To provide protocol clarity based on the responses to the questions received from EU CTA review
 
Section 10.11 Added ASA Physical Status Classification System as a reference.
 
Justification: To provide protocol clarity based on the responses to the questions received from EU CTA review
 
References: Added American Society of Anesthesiologists. Statement on ASA Physical Status Classification System. 2020.
 
Justification: To provide protocol clarity based on the responses to the

Document	Version Date	Summary of Changes and Rationale
		
questions received from EU CTA review
 
List of abbreviations updated.
 
Justification: Added appendix 11

## 1. PROTOCOL SUMMARY

### 1.1. Synopsis

#### Protocol Title:

A Phase 2a Double-Blind, Placebo-Controlled Study to Evaluate the Efficacy, Safety, and Tolerability of KAN-101 In Participants With Celiac Disease

#### Brief Title:

A Study of the Efficacy, Safety, and Tolerability of KAN-101 in Participants With Celiac Disease

#### Regulatory Agency Identification Number(s):

US IND Number:	19492
EudraCT/EU CT Number:	2023-507240-37-00
ClinicalTrials.gov ID:	NCT 06001177
Pediatric Investigational Plan Number:	NA
Protocol Number:	KAN-101-03
Phase:	Phase 2a

#### Rationale:

The sponsor is initiating this Phase 2a study of KAN-101 in adult participants with celiac disease (CeD) to investigate the ability of KAN-101 to protect intestinal mucosa from gluten-induced histological damage.

#### Objectives, Endpoints, and Estimands:

Objectives	Endpoints	Estimands
Primary:	Primary:	Primary:

Assess the ability of KAN-101 to attenuate gluten challenge (GC)-induced changes in duodenal histology as measured by changes in villus-height:crypt depth (Vh:Cd) ratio after a 2-week GC.

	

Changes from baseline in Vh:Cd ratio as assessed by esophagogastroduodenoscopy (EGD) with biopsy after 2-week GC (at Day 29)

	
Estimand 1: The primary estimand is the hypothetical estimand, which estimates the treatment effect of KAN-101 vs placebo for change from baseline in the ratio of Vh:Cd under the scenario of no intercurrent events. It includes the following 5 attributes:
 

Population: Participants who receive all 3 doses of study intervention and complete at least 7 days of GC.

Variable: the ratio of Vh:Cd change from baseline at Day 29.

Treatment conditions: KAN-101 or placebo.

Intercurrent Events: Prohibited medication. All data collected after any intercurrent events will be excluded.

Objectives	Endpoints	Estimands
		
 
• Population level summary: The LSM difference of the change from baseline in the ratio of Vh:Cd between KAN-101 and placebo.
 

Secondary:	Secondary:	Secondary:

 
• Examine the impact of KAN-101 on biomarker response (interleukin-2 [IL-2]) in peripheral blood following GC
 
	
 
• IL-2 change from Day 15 (first day of GC) pre GC to Day 15 post GC.
 
	
Estimand 2 is the hypothetical estimand, which estimates the treatment effect of KAN-101 vs Placebo for IL-2 under the scenario of no intercurrent events. It includes the following 5 attributes:
 
 
• Population: Participants who receive all 3 doses of study intervention and complete at least 7 days of GC.
 
• Variable: log transformed IL-2 change from pre GC to post GC at Day 15.
 
• Treatment conditions: KAN-101 or placebo.
 
• Intercurrent Events: Prohibited medication, incomplete GC on Day 15. All data collected after any intercurrent events will be excluded.
 
• Population level summary: The least-squares mean (LSM) difference of the change from pre GC to post GC at Day 15 (log transformed) between KAN-101 and placebo.
 

 
• Determine the effects of KAN-101 on histologic features (intraepithelial lymphocytes [IELs] density) in duodenum biopsies following 2-week GC.
 
	
 
• Changes from baseline in IEL density in duodenum biopsy after 2-week GC (at Day 29)
 
	
Estimand 3 is the hypothetical estimand, which estimates the treatment effect of KAN-101 vs placebo for change from baseline in duodenal IEL density under the scenario of no intercurrent events. It includes the following 5 attributes:
 
 
• Population: Participants who receive all 3 doses of study intervention and complete at least 7 days of GC.
 
• Variable: IEL change from baseline at Day 29.
 
• Treatment conditions: KAN-101 or placebo.
 
• Intercurrent Events: Prohibited medication. All data collected after any intercurrent events will be excluded.
 
• Population level summary: The LSM difference of the change from baseline in IEL between KAN-101 and placebo.
 


 
• Assess the safety and tolerability of KAN-101 in participants with CeD.
 
	
 
• Incidence and severity of treatment emergent AEs as assessed by the Common Terminology Criteria for Adverse Events (CTCAE) v6.0 (or higher)
 
	Not applicable.
	
 
• Incidence and titer of KAN-101 anti-drug antibodies (ADA)
 
	Not applicable.

 
• Assess the pharmacokinetics (PK) of multiple doses of KAN-101 in participants with CeD.
 
	
 
• Plasma concentration of KAN-101, and associated KAN-101 parameters: <math>AUC_{inf}</math>, <math>AUC_{last}</math>, <math>C_{max}</math>, <math>T_{max}</math> and <math>t_{1/2}</math>
 
	Not applicable.

**Dose Selection:** Based on KAN-101-01 study results, 0.6 mg/kg of KAN-101 administered in 3 doses 3 days apart, will be evaluated. The frequency of dosing in the study is supported by the nonclinical, experimental autoimmune encephalomyelitis (EAE) mouse model that demonstrated that dosing every 3 days over one week was more effective than once per week dosing. Clinical biomarker data from the KAN-101-01 first-in-human (FIH) study also suggest that this dosing regimen is effective and appropriate in adults with CeD.

**Overall Design:**

Study KAN-101-03 is a multi-center, double-blind, placebo-controlled Phase 2a study to examine whether KAN-101 confers protection from GC-induced histological changes in the duodenum and to further evaluate the safety/tolerability of KAN-101 in adult participants ( $\geq 18$  years) with CeD. Fifty-two participants (26 participants per arm) will be randomized 1:1 to the following arms: **0.6 mg/kg KAN-101 (Arm 1)** and **Placebo (Arm 2)**. This study comprises 4 periods:

**Screening period:** The study screening period is  $\leq 42$  days. During the screening period, eligibility will be confirmed by EGD with duodenal biopsy. The EGD with biopsy will only be performed once all other inclusion criteria are fulfilled. Histology results must be received prior to dosing to confirm eligibility.

**Treatment period:** The study treatment period is 7 days (Day 1 to Day 7). Study intervention will be administered to enrolled participants in the clinic intravenously (IV) on Day 1, Day 4, and Day 7. Post infusion each treatment day, participants will be monitored in the clinic for at least 4 hours for adverse reactions.

**GC:** Participants will undergo a 2-week GC in which they will ingest 9 g/day of gluten protein in the form of 12 g vital wheat gluten. All participants will return to the clinic on Day 15 for the first day of GC. The Day 15 GC will be performed in the clinic under supervision and blood samples will be collected at least 5 minutes prior to GC and 4 hours after the completion of the Day 15 GC for biomarker assessment. Materials will be sent home with the participant to complete the GC daily for the next 2 weeks (through Day 28). The study site will call the participant on Day 16 and Day 21 to collect data on any AEs or CM over the telephone. Symptom monitoring and compliance with the GC will be conducted via eDiary.

**Observation and Follow-up period:** Participants will be observed and followed for safety for the duration of the study (42 days [Day 1 to Day 42]). The second EGD with duodenal biopsy will be conducted on Day 29. Participants will return to the clinic on Day 42 for a final follow-up visit including safety assessment and labs, celiac serology, and exploratory biomarker sample collections.

If participants are unable to return to the clinic for protocol-specified visits, alternative methods for safety assessments and data collection may be employed to ensure the safety of the trial participants when appropriate.

**Data Safety Monitoring Board (DSMB):** This study will utilize a DSMB that will be composed of at least 2 physicians, one of which will be a CeD medical expert, and 1 biostatistician. DSMB members will be independent from the conduct of the study. The DSMB safety monitoring plan will be detailed in the DSMB charter. The primary responsibility of the DSMB is to safeguard study participants by reviewing and assessing the cumulative clinical safety data being collected during the performance of the study. The DSMB will meet periodically throughout the study to review cumulative safety data.

**Number of Participants:** It is anticipated that the study will enroll approximately 52 treated participants.

**Study Population:** Key inclusion and exclusion criteria are listed below.

### **Key Inclusion Criteria**

Participants must meet the following key inclusion criteria to be eligible for enrollment into the study:

1. Adults aged 18 to 70 years inclusive.
2. Previously documented diagnosis of CeD based on positive serology (eg, tissue transglutaminase IgA antibody and/or DGP IgG) AND intestinal histology consistent with  $\geq$  Marsh Type II or with evidence of villous atrophy.
3. HLA-DQ2.5 genotype (HLA-DQA1\*05 and HLA-DQB1\*02) (homozygotes or heterozygotes).
4. Negative or weak positive for transglutaminase IgA and negative or weak positive for DGP-IgA/IgG during screening.
5. Have followed a gluten-free diet for  $\geq$ 12 months immediately prior to study entry (self-reported).
6. Screening intestinal biopsy demonstrating Vh:Cd ratio of 2.3 or higher.

### **Key Exclusion Criteria**

Participants with any of the following key characteristics/conditions will be excluded:

1. Refractory CeD, defined as severe persistent or recurrent malabsorptive signs or symptoms with substantial villous atrophy (eg, documented Marsh score 3c in source data) despite strict adherence to a GFD for at least 12 months in absence of other disorders.
2. Selective IgA deficiency.
3. Positive for HLA-DQ8 genotype (DQA1\*03, DQB1\*0302) even if DQ2.5 is also present.

CONFIDENTIAL

4. Known wheat allergy.
5. Diagnosis of type-I diabetes.
6. History of dermatitis herpetiformis.
7. Pregnant or breastfeeding.
8. Known history of severe hypersensitivity reactions or anaphylaxis to gluten.
9. Active gastrointestinal disease other than CeD (eg, inflammatory bowel disease, any forms of colitis except well-controlled microscopic colitis, uncontrolled IBS, peptic ulcer disease, eosinophilic esophagitis, and active GI infections).
10. Previous treatment with tolerance-inducing therapies for CeD.

### **Study Arms and Duration:**

Study Intervention(s)		
	blinded manner per country and site requirements.	

IMP or NIMP/AxMP: Investigational medicinal product, Non investigational medicinal product, auxiliary medicinal product, IPM: Investigational product manual

### Statistical Methods:

Sample Size Determination: The total sample size is expected to be approximately 52 treated participants.

A total sample size of 26 participants in each treatment group will have approximately 94% power to detect a difference in LSM of 0.50 in change in ratio of Vh:Cd between treatment and placebo, assuming that the common standard deviation is 0.45. Details of the analyses will be described in the statistical analysis plan.

### Analysis Population

All participants who receive any portion of study intervention will be included in the Safety Analysis Set. All safety data will be summarized for participants in the Safety Analysis Set.

The Full Analysis Set will consist of all randomized participants who receive all 3 doses of study intervention and complete at least 7 days of GC.

The Per Protocol Set will include all participants from the FAS who complete all 14 days of GC and biopsies (Baseline [Day 1] and Day 29) and without major protocol violations that might affect study intervention on the primary endpoint. The PPS will be used in sensitivity analyses of the primary and secondary endpoints.

The Pharmacokinetic Analysis Set will contain all participants who received any portion of study intervention and have at least one post-dose drug concentration value.

### Interim Analysis:

A planned IA will be performed when approximately 13 participants from each group have completed the Day 29 visit and histology assessments.

Unless a safety concern arises, no decision to stop the trial will be made based on this interim analysis. The results of the IA will be used for future strategic planning for the overall KAN-101 program.

### Primary Statistical Analysis

The primary endpoint change from baseline in the ratio of Vh:Cd will be analyzed using an analysis of covariance ANCOVA model with treatment as a factor and baseline as a covariate. Descriptive statistics will be used in general to summarize study results, ie, statistics for continuous variables will include number of observations, mean, standard

[figure not shown]
CONFIDENTIAL

deviation, median, first, second, and third quartiles, minimum, and maximum; statistics for binary and categorical variables will include count and percentage. The CV, GM will also be included for continuous endpoints, where appropriate.

**Ethical Considerations:**

The overall potential benefit/risk of KAN-101 is considered favorable. Considering the measures and mitigations to minimize risk to study participants, the potential risks identified in association with participation in the study and with KAN-101 are justified by the anticipated benefits that may be afforded to participants with CeD.

## 1.2. Schema

### 1.3. Schedule of Activities

The SoA table provides an overview of the protocol visits and procedures. Refer to the [STUDY ASSESSMENTS AND PROCEDURES](#) section of the protocol for detailed information on each procedure and assessment required for compliance with the protocol.

The investigator may schedule visits (unplanned visits) in addition to those listed in the SoA table, in order to conduct evaluations or assessments required to protect the well-being of the participant.

**Table 1. Schedule of Assessments**

Abbreviations used in this table may be found in Appendix 12 .	Scr.	Treatment Period				Gluten Challenge (Day 15 to 28)			Biopsy	FU	ET	Notes
Visit Identifier	V1	V2	V3	V4	V5	V6	V7	V8	V9	ET		

• Day relative to start of study intervention (Day 1).

• See Section 8.4.3 for follow-up AE and SAE assessments.

• D16 and D21 are phone call visits (See Section 8.1.1) for collection of AEs and concomitant medications.

Type (Site or Phone Call)	Site	Site	Site	Site	Site	Phone	Phone	Site	Site	Site		
Study Day (D)	Up to -42 days	D1	D4	D7	D15	D16	D21	D29	D42	ET		
Visit Window (days)					+2	±2	+3	+3				
Screening Assessments												
Informed consent	X											

• Informed consent should be obtained prior to undergoing any study-specific procedures. See Section 10.1.3 for additional information.

Medical history & demographics	X											

• Includes disease history (symptoms at diagnosis and length of time on GFD) and GC history (within previous 12 months).

Inclusion/exclusion	X	X										
HIV, HBV, HCV testing	X											

• See Exclusion Criterion #19 (See Appendix 2 for additional information).

HLA genotype	X											

• HLA genotype will be assessed via central laboratory. For rescreening, HLA does not need to be repeated.

CONFIDENTIAL

CT02-GSOP Clinical Protocol Template Phase 1 2 3 4 (14 April 2023)

**Table 1. Schedule of Assessments**

Abbreviations used in this table may be found in Appendix 12 .	Scr.	Treatment Period				Gluten Challenge (Day 15 to 28)			Biopsy	FU	ET	Notes	
Visit Identifier	V1	V2	V3	V4	V5	V6	V7	V8	V9	ET		
 
Day relative to start of study intervention (Day 1).
 
See Section 8.4.3 for follow-up AE and SAE assessments.
 
D16 and D21 are phone call visits (See Section 8.1.1) for collection of AEs and concomitant medications.
 
	
Type (Site or Phone Call)	Site	Site	Site	Site	Site	Phone	Phone	Site	Site	Site			
Study Day (D)	Up to -42 days	D1	D4	D7	D15	D16	D21	D29	D42	ET			
Visit Window (days)					+2	±2	+3	+3					
CeD serology	X								X	X		
 
CeD serology (tTG-IgA and DGP IgG) will be assessed via central laboratory (see Appendix 2 for additional information). For rescreening, CeD serology only needs to be repeated if >3 months have elapsed from last assessment.
 
	
12-lead ECG	X											
 
Not required for participants who have had an ECG within 3 months prior to screening.
 
	
Set up eDiary	X												
Clinical Procedures													
Physical examination	X							X	X	X		
 
See Section 8.3.5.
 
	
Pregnancy test	X	X			X			X	X	X		
 
Test at screening must be serum; serum or urine tests are acceptable at other visits. Screening and pre-dosing pregnancy tests must be negative before study intervention is administered. D15 pregnancy test must be negative before 2-week GC is initiated. See Section 8.3.6.
 
	
Contraception check	X	X	X	X	X			X	X	X		
 
See Section 5.3.1
 
	
Vital signs	X	X	X	X	X			X	X	X		
 
At screening only, includes height and weight.
 
Vital signs (pulse rate, temperature, respiratory rate, diastolic and systolic blood pressure) should be assessed before, during, and after dosing and before sample collection. See Section 8.3.2 for additional information.
 
	

CONFIDENTIAL

CT02-GSOP Clinical Protocol Template Phase 1 2 3 4 (14 April 2023)

Page 23

**Table 1. Schedule of Assessments**

Abbreviations used in this table may be found in Appendix 12 .	Scr.	Treatment Period				Gluten Challenge (Day 15 to 28)			Biopsy	FU	ET	Notes
Visit Identifier	V1	V2	V3	V4	V5	V6	V7	V8	V9	ET		
 
Day relative to start of study intervention (Day 1).
 
See Section 8.4.3 for follow-up AE and SAE assessments.
 
D16 and D21 are phone call visits (See Section 8.1.1) for collection of AEs and concomitant medications.
 

Type (Site or Phone Call)	Site	Site	Site	Site	Site	Phone	Phone	Site	Site	Site		
Study Day (D)	Up to -42 days	D1	D4	D7	D15	D16	D21	D29	D42	ET		
Visit Window (days)					+2	±2	+3	+3				
Prior/concomitant meds/procedures, incidental gluten exposure	X	X	X	X	X	X	X	X	X			
 
See Section 6.9 for additional information.
 
Incidental gluten exposure checked daily; entered into eDiary and reviewed at study visits.
 

EGD with biopsy (approx. 6 duodenal biopsies)	X							X		X		
 
EGD should only be performed after the participant has qualified with all other inclusion/exclusion criteria.
 
For rescreening, EGD does not need to be repeated if 1) <3 months have elapsed from last screening assessment, 2) the participant has continued GFD and 3) the participant has not undergone a GC.
 
Only participants who have completed all 3 doses of study intervention and at least 7 days of GC should undergo EGD with biopsy at D29 or at ET visit (if participant discontinues prior to D29).
 

PGIS		X			X			X	X	X		
 
Day 1 PGIS should be completed pre-dose (at least 5 minutes prior to infusion).
 

PGIC					X			X	X	X		
GC					D15-28 daily							
 
GC completed in clinic on D15 and at home for the next 13 days (D16 to D28).
 
Participants who withdraw from treatment and do not receive 3 full doses should not receive GC.
 

CDSD v2.1	To be completed daily											
 
PRO (CDSD® v2.1) will be completed via eDiary for at least 7 consecutive days during screening.
 
For re-screening: CDSD v2.1 only needs to be repeated if >3 months have elapsed from end of last PRO administration.
 

CONFIDENTIAL

CT02-GSOP Clinical Protocol Template Phase 1 2 3 4 (14 April 2023)

Page 24

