- PGIS is a PRO questionnaire designed to assess the patient's impression of disease severity over the past week (see [Appendix 2.3](#)) that is collected at baseline (Day 1), Day 15, 29, 42, or ET visit.
- Change from baseline at each timepoint = observed value at each timepoint – baseline. Baseline is the last non-missing value up to Day 1.
- The observed value in PGIC

- PGIC is a PRO questionnaire designed to assess the patient's impression of the overall change in participant's celiac disease since receiving study intervention (see [Appendix 2.4](#)) that will be collected at Days 15, 29, 42, or ET visit.
- Change from baseline in incidence and titer of tTG IgA and DGP IgG at Day 42.
- Other exploratory biomarkers may be analyzed at a later date.

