5.3.2.2. PGIC

PGIC will be descriptively summarized as stated in Section 5.

The analysis will be performed for all collected data as stated in Section 5.

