Appendix 1. Summary of Efficacy/Exploratory Analyses

Endpoint	Analysis Type	Population	Analysis Model
Change from baseline in Vh:Cd ratio at Day 29	Summary	FAS	N/A
	Main analysis	FAS	ANCOVA with terms treatment, baseline
	Sensitivity/supplementary analysis	PPS, SAS	ANCOVA with terms treatment, baseline
GC IL-2 (log-transformed) change from Day 15 pre-GC to Day 15 post GC	Summary	BAS	N/A
	Analysis	BAS	ANCOVA with terms treatment, baseline
	Sensitivity/supplementary analysis	PPS, SAS	ANCOVA with terms treatment, baseline
Changes from baseline in IEL density in duodenum biopsy after 2-week GC (at Day 29)	Summary	FAS	N/A
	Analysis	FAS	ANCOVA with terms treatment, baseline
	Sensitivity/supplementary analysis	PPS, SAS	ANCOVA with terms treatment, baseline

Endpoint	Analysis Type	Population	Analysis Model
CDSD change from baseline at each timepoint	Summary	FAS	N/A
	Analysis	FAS	ANCOVA with terms treatment, baseline
	Sensitivity/supplementary analysis	PPS, SAS	ANCOVA with terms treatment, baseline
CDSD 1-Day, 3-Day, 7-Day Nausea Score and Vomiting Frequency and change from baseline at each timepoint post-gluten challenge	Summary	FAS	Observed cases
	Analysis	FAS	All data collected will be included regardless of intercurrent events. Missing data will not be imputed. Wilcoxon Signed-rank test for change from baseline within each group
	Analysis	FAS	All data collected will be included regardless of intercurrent events. Missing data will not be imputed. Mann-Whitney U test (Wilcoxon)

Endpoint	Analysis Type	Population	Analysis Model
			Rank Sum test) for comparison of placebo vs KAN group for change from baseline
PGIS change from baseline at each timepoint	Summary	FAS	N/A
	Analysis	FAS	ANCOVA with terms treatment, baseline
PGIC at each timepoint	Summary	FAS	N/A
	Analysis	FAS	ANOVA with term treatment
Marsh- Oberhuber score	Summary	FAS, PPS, SAS	N/A

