Appendix 2. Data Derivation Details

Appendix 2.1. Definition and Use of Analysis Windows in Reporting

Analysis windows will be used for PROs and vital signs, and laboratory tests.

If more than one observation from the same participant falls into the same analysis window, the value closest to the targeted day will be used as the observation for that visit. All observations will, however, be included in the listings.

Table 3 Analysis Windows for PGIS and PGIC

Visit Label	Targeted Day	Analysis window for data sets
Baseline (Screening up to first dosing date)	Day 1	Last observation up to and including first dosing date
Day 15	Day 15	After last dose – First day of GC
Day 29	Day 29	Second day of GC – Day 35
Day 42	Day 42	Day 36 – end of study

Table 4 Analysis Windows for Vital Signs

Visit Label	Targeted Day	Analysis window for data sets
Baseline (Screening up to first dosing date)	Day 1	Last observation up to first dosing
Day 1 during dosing	Day 1 during dosing	Start of Day 1 dosing to end of Day 1 dosing
Day 1 after dosing	Day 1 after dosing	End of Day 1 dosing to end of Day 1
Day 4 before dosing	Day 4 pre-dosing	Day 2 - Day 4 pre-dosing
Day 4 during dosing	Day 4 during dosing	Day 4 start of dosing - Day 4 end of dosing
Day 4 after dosing	Day 4 after dosing	Day 4 end of dosing - end of Day 4
Day 7 before dosing	Day 7 pre-dosing	Day 5 - Day 7 pre-dosing
Day 7 during dosing	Day 7 pre-dosing	Day 7 start of dosing - Day 7 end of dosing
Day 7 after dosing	Day 7 after dosing	Day 7 end of dosing - end of Day 7
Day 15	Day 15 pre-GC	Day 8 - pre-GC of first GC day
Day 29	Day 29	After GC of first GC day – Day 35
Day 42	Day 42	Day 36 – end of study

Table 5 Analysis Windows for Laboratory Tests

Visit Label	Targeted Day	Analysis window for data sets
Baseline (Screening up to first dosing date)	Day 1	Last observation up to first dosing
Day 4	Day 4 pre-dosing	Day 1 after dosing - Day 4 pre-dosing
Day 7	Day 7 pre-dosing	Day 4 after dosing - Day 7 pre-dosing
Day 15	Day 15 pre-GC	Day 7 after dosing - pre-GC of first GC day
Day 29	Day 29	post-GC of first GC day – Day 35
Day 42	Day 42	Day 36 – end of study

Table 6 Analysis Windows for ADA

Visit Label	Targeted Day	Analysis window for data sets
Baseline (Screening up to first dosing)	Day 1 pre-dosing	Last observation prior to first dosing date
Day 7	Day 7 pre-dosing	Day 2 - Day 7 pre-dosing
Day 29	Day 29	Day 8 – Day 35
Day 42	Day 42	Day 36 – end of study

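### Exploratory global scales: the SAP does not tie the PGIS baseline to before the first infusion, and its PGIC comparison leaves the Day 1 PGIS unused; both are minor and need only SAP wording

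*Protocol*

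**What the plan says.** **Collection.** Protocol Table 1 schedules PGIS on Days 1, 15, 29 and 42 and at early termination, and PGIC at the same visits except Day 1. On timing it says: "Day 1 PGIS should be completed pre-dose (at least 5 minutes prior to infusion". No screening or post-infusion PGIS is scheduled.

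**PGIS baseline.** SAP 2.3: "Baseline is the last non-missing value up to Day 1". SAP Appendix 2.1, Table 3: "Last observation up to and including first dosing date". Neither requires the answer to precede the infusion.

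**Other baselines in the SAP.** Tables 4 and 5 (vital signs, laboratory tests): "Last observation up to first dosing". Tables 6 and 7 (ADA, biopsy): "Last observation prior to first dosing date". The CDSD baseline in SAP 2.3 excludes Day 1 altogether.

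**More than one record in a window.** SAP Appendix 2.1: "the value closest to the targeted day will be used as the observation for that visit". For CDSD, SAP 5.3.2 adds that the earliest of several same-day records is used. PGIS has no such rule.

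**Models.** SAP 5.3.2.1 analyses PGIS change by ANCOVA with baseline as covariate. For PGIC, Appendix 1 gives "ANOVA with term treatment", following the general rule in SAP 4.2.1 for endpoints without a baseline. The body text says "PGIC will be descriptively summarized as stated in Section 5", then refers to an analysis of all collected data without naming a model.

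**The concern.** A baseline used as a covariate, and subtracted to form a change score, should come before treatment. The Table 3 window is set by date and covers the whole dosing day, so it cannot tell a pre-infusion answer from a post-infusion one. Because it takes the last answer, it prefers the later of the two. If early symptoms after the infusion were more frequent on KAN-101, their PGIS baselines would be raised, and later change would look better on KAN-101 without any benefit.

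For PGIC, the participant's severity before treatment is already scheduled for collection but is not used. In a trial of 52, adjusting for a covariate related to the outcome can shorten the interval. A reader of 5.3.2.2 alone would also not know that a between-arm model is planned.

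**Working it through.** The documents give no SD, correlation or power for PGIS or PGIC, so there is no stated figure to reproduce.

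**1. Which Day 1 answer becomes the baseline**

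| Day 1 PGIS answers | Value selected by SAP Table 3 |
|---|---|
| One, pre-dose (as scheduled) | The pre-dose answer |
| One, entered late after the infusion | The post-infusion answer |
| One before and one after the infusion | The post-infusion answer (last observation) |

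The closest-to-target rule does not help, because both answers fall on the target day. The SAP 2.3 wording gives the same selections. A pre-dose cut-off would change rows 2 and 3 only.

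**2. Size of the effect on PGIS**

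Assume that a higher score is worse and that there is no true effect. Let a share f of the KAN-101 arm, over and above placebo, have its baseline raised by s points, and let β be the slope of follow-up on baseline.

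- The KAN-101 mean baseline rises by f × s.
- The ANCOVA difference in change equals the follow-up difference minus β times the baseline difference. It therefore shifts by −β × f × s.
- The unadjusted mean change, also summarised under SAP 5.3.2.1, shifts by −f × s.

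None of f, s or β is in the documents. For illustration only, take s = 1 point:

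- β = 0.3, f = 5%: 0.3 × 0.05 × 1 = 0.015 points.
- β = 0.7, f = 20%: 0.7 × 0.20 × 1 = 0.14 points.
- f = 0 (all answers pre-dose): zero.

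SAP 2.3 describes PGIS as covering the past week. An answer given hours after the infusion still refers mostly to earlier days, so s is probably damped.

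**3. Precision of PGIC**

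Inputs: 26 per arm (protocol 9.6). Its uneven dropout example gives 26 × 0.8 = 20.8 and 26 × 0.6 = 15.6, or about 21 and 16, so N = 37. The correlation r between Day 1 PGIS and later PGIC is assumed.

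- Variance ratio, ANCOVA to ANOVA: (1 − r²) × (N − 3)/(N − 4).
- Interval-width ratio: the square root of that, times t(0.975, N − 3)/t(0.975, N − 2).
- Example, N = 37, r = 0.3: 0.91 × 34/33 = 0.938; square root 0.968; times 2.032/2.030 gives 0.969.

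| r | Width ratio, 21 vs 16 | Width ratio, 26 vs 26 |
|---|---|---|
| 0 | 1.016 | 1.011 |
| 0.1 | 1.011 | 1.006 |
| 0.2 | 0.996 | 0.990 |
| 0.3 | 0.969 | 0.964 |
| 0.4 | 0.931 | 0.926 |
| 0.5 | 0.880 | 0.875 |

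Break-even on variance is at r² = 1/(N − 3), so |r| = √(1/34) = 0.17 for N = 37 and √(1/49) = 0.14 for N = 52.

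**The case against.** **The baseline problem needs a departure from the protocol.** One Day 1 PGIS is scheduled, and it is due before the infusion. The window has to include the dosing date because the only baseline answer falls on it. This stands: the SAP permits a post-infusion baseline but does not direct one. It does not remove the point. A baseline rule exists for imperfect data, PROs are entered by eDiary (protocol 8.2.3), participants stay at least 4 hours after the infusion (protocol 6.1.1), and the SAP already foresaw repeat same-day CDSD records and chose the earliest.

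**The direction of bias is not established.** A reader might infer it from protocol 2.2.3, which reports more participants with GI adverse events on drug than on placebo in the first-in-human study. That excess is for all dose levels pooled and is not tied to the hours after a first infusion, and the same section reports no meaningful safety differences among groups. Protocol 6.1.1 does foresee nausea or vomiting after Day 1 dosing. The documents support that bias towards KAN-101 could occur, not that it would.

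**PGIC has no baseline by construction.** It asks about change since study intervention, and the treatment-only ANOVA follows the prespecified rule. This stands: the comparison is unbiased under randomisation, and chance imbalance is already reflected in its interval. Participants have been gluten-free for at least 12 months, with limited serology and a Vh:Cd ratio of at least 2.3. Day 1 severity may therefore vary little and r may be low.

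**Adjustment can cost participants.** SAP 4.3 does not impute, so anyone without a pre-dose PGIS leaves both adjusted models. If 20% of 21 were lost (about 4), 17 vs 16 would remain. The standard error would rise by √(1/17 + 1/16)/√(1/21 + 1/16) = 0.348/0.332, or about 5%, more than the 3% gain at r = 0.3. This stands as a cost, although 20% is itself only an assumption.

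**Conclusion.** Two small weaknesses hold, both confined to exploratory endpoints that, by protocol 9.4.4, may not be described in the CSR.

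1. The PGIS baseline rule is looser than the protocol's pre-dose instruction and than the SAP's other baseline rules. The bias is zero if all Day 1 answers are pre-dose. Otherwise it is about slope × affected share × shift, damped by past-week recall, and the documents do not allow it to be estimated.
2. The PGIC model leaves out a covariate that is already collected. The gain is about 3% to 12% of interval width for assumed correlations of 0.3 to 0.5. Below about 0.17 the loss is at most 1% to 2%.

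A reader might also infer that the PGIC comparison is biased, or that 5.3.2.2 rules out a between-arm test and so contradicts Appendix 1. The documents support neither. The first is a matter of efficiency. On the second, 5.3.2.2 never says that PGIC is descriptive only; it is incomplete because it names no model.

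**What to change.** - **SAP 2.3 and Appendix 2.1, Table 3:** define the PGIS baseline as the last answer before the start of the first infusion. List later answers on that day, but do not use them as baseline.
- **SAP 5.3.2.2 and Appendix 1:** state the same PGIC analysis in both places, namely ANCOVA by timepoint with treatment and pre-dose Day 1 PGIS. Settle this before unblinding.

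The cost is SAP wording, one degree of freedom in the PGIC model, and the loss from both adjusted models of participants who have no pre-dose PGIS. Report how many these are in each arm. No new data are needed.
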